4.4 Sample size calculation

Sample size is estimated on the basis of sample availability and literature. An important study is by Torres et al. (5), where they included 48 controls and 73 women with PCOS. In figures 1a and 1b they show that with these numbers they find a significant difference between the operational taxonomic units (OTUs) and the

Faith PD. The Faith PD is a measure of diversity based on the phylum of the bacteria. There are several studies that show no difference with a small sample size (n=10-30), but the study by Lindheim et al.(4) shows that with 24 PCOS women and 19 controls a decreased diversity was found with also significantly decreased abundances of *Tenericutes* and *Bacteroidetes*. Due to the novelty of this field of study, the pilot data set is not publicly accessible. In order to analyze the differences in microbiome composition between gut and vaginal microbiome, between study and control group, 100 patients will be included (n=50 with a BMI > 30 kg/m² and n=50 with BMI 19-25 kg/m²) in study group. Also, 100 healthy women will be included in the control group.

TREATMENT OF SUBJECTS

5.1 Investigational product/treatment

Not applicable

5.2 Use of co-intervention (if applicable)

Not applicable

5.3 Escape medication (if applicable)

Not applicable

6 INVESTIGATIONAL PRODUCT

6.1 Name and description of investigational product(s)

Not applicable

6.2 Summary of findings from non-clinical studies

Not applicable

6.3 Summary of findings from clinical studies

Not applicable

6.4 Summary of known and potential risks and benefits

Not applicable

6.5 Description and justification of route of administration and dosage

Not applicable

6.6 Dosages, dosage modifications and method of administration

Not applicable

6.7 Preparation and labelling of Investigational Medicinal Product

Not applicable

6.8 Drug accountability

Not applicable

7 NON-INVESTIGATIONAL PRODUCT>**7.1 Name and description of non-investigational product(s)**

Not applicable

7.2 Summary of findings from non-clinical studies

Not applicable

7.3 Summary of findings from clinical studies

Not applicable

7.4 Summary of known and potential risks and benefits

Not applicable

7.5 Description and justification of route of administration and dosage

Not applicable

7.6 Dosages, dosage modifications and method of administration

Not applicable

7.7 Preparation and labelling of Non Investigational Medicinal Product

Not applicable

7.8 Drug accountability

Not applicable

8 METHODS

8.1 Study parameters/endpoints

8.1.1 Main study parameter/endpoint

- Differences in community structure of the gut microbiome between PCOS patients and controls as such and its diagnostic and metabolic characteristics.

8.1.2 Secondary study parameters/endpoints

- Differences in community structure in the vaginal microbiome between PCOS patients and controls as such and its diagnostic and metabolic characteristics.
- Differences and similarities in community structure of the vaginal- and gut microbiome in PCOS patients
- Differences and similarities between the vaginal- and gut microbiome composition between overweight/obese and lean patients (with/without PCOS)
- Metabolic profiles from different phenotypes of PCOS

8.1.3 Other study parameters (if applicable)

Not applicable

The analyses for differences in community structure in the gut and vaginal microbiome are explained here:

A common strategy is to group reads at some level of similarity into representative sequences of hypothetical species called Operational Taxonomic Units (OTUs), where all reads within, 97% similarity are clustered together and represented by a single OTU sequence. This is done because bacterial taxonomy is incomplete and there are sequencing errors in the Next Generation Sequencing (NGS) reads.

Alpha diversity refers to the number of different taxa within a specific community; it indicates the richness of the gut microbiome. Beta diversity is a measure of how comparable the gut microbiome is between healthy people and PCOS patients. Shannon diversity index is a way to measure the diversity of species in a community. The higher the value of H, the higher the diversity in a particular community. Another measure of alpha diversity could be the species richness, which is the count of the number of species or OTUs present in that sample.

UniFrac will be used to compare the (dis-)similarities among the microbial communities samples (beta-diversity). Unweighted UniFrac analyses is based on presence/absence of difference taxa and abundances and weighted UniFrac will take the abundances of different taxa into consideration.

8.2 Randomisation, blinding and treatment allocation

Not applicable

8.3 Study procedures

Patients are eligible for the study after they are diagnosed with PCOS at the regular COLA screening. The abbreviation COLA stands for: Cycle disorders, Oligomenorrhea and Amenorrhea. During the regular COLA screening visit, patients will undergo a physical examination, including a transvaginal ultrasound. Three to four weeks after the COLA screening patients will receive their COLA screening results. Patients who are diagnosed with PCOS and are eligible for the study will be informed about the details of the study. Patients will receive a patient information leaflet with the informed consent form, together with the contact information of the clinical coordinator in case they might have any remaining questions.

The main investigator will contact them by phone 1 week after their appointment for their COLA screening result and ask if they are interested in participating in the study. If the patient agrees to participate, the material for stool sample collection will be sent to her. Patients will be instructed to collect the stool sample after signing the informed consent (preferably on the day of the second appointment, but no more than 2 days before) On the day of the second appointment, the researcher will sign the informed consent and provide a copy to the patient. A vaginal swab will be obtained by the physician and the stool sample will be handed in by the patient.

Vaginal samples and blood samples will be collected in the non-menstrual period during the appointment. Patients will be asked to fill in an online Food Frequency Questionnaire (max 45min).

Also, PCOS patients in the COLA database who are eligible will be approached to participate in this study. They will be contacted by phone, and if they are interested in participation, a PIF will be sent to their home address.

Participants in the control group will be informed by the main investigator. When they meet the inclusion criteria and they decide to participate in the study, the same COLA screening will be conducted, in combination with this study protocol.

COLA screening volunteers who have already agreed to be approached for any future studies, will receive the PIF and be asked to participate in this study. These candidates are healthy and have a regular menstrual cycle.

Online advertisement will be published to recruit volunteers.

After collection the vaginal swab and stool sample will be split in different portions to be analysed using the 16S rRNA gene sequencing. In both the stool and vaginal swab samples the following parameters will be measured: both the microbiome profile patterns (three different groups of microorganisms: (1) Firmicutes/ Actinobacteria/ Verrucomicrobia (2) Bacteroidetes and (3) Proteobacteria) by the NGS and another high throughput technique for the Lactobacillus, Staphylococcus, E coli and Bacillus RG4 composition as percentage of the total microbiome content.

16S ribosomal RNA amplicon sequencing

Both gut and vaginal microbiome will be analysed by using 16S ribosomal RNA sequencing (rRNA). For each sample the V4 hypervariable region of the 16S rRNA gene will be amplified by polymerase chain reaction (PCR) with primers. The steps in the PCR process are as follow and each step occurs at a different temperature. First denaturation at 94°C occurs and the two DNA strands get separated out. Then amplification at different temperatures occurs. Finally, the enzyme Polymerase is added which make the primers extend along the length of the DNA strand.

Laboratory measurements includes: estradiol, total testosterone, androstenedione, dyhydroepiandrosterone (DHEA), dehydroepiandrosterone sulfate (DHEAS), dehydrotestosterone (DHT), serum cortisol, thyroid-stimulating hormone (TSH), prolactin, insulin, anti-Muellerian hormone (AMH), sex hormone-binding globulin (SHBG), serum luteinizing hormone (LH), follicle-stimulating hormone (FSH), 17-hydroxyprogesterone (17OH-P), plasma total cholesterol, high-density lipoprotein (HDL)- cholesterol, triglycerides and glucose. These laboratory measurements are already included in the COLA screening. Addition measurements that will be obtained include but will not limited to: LH, FSH, estradiol, progesteron, hsC-reactive protein (CRP), interleukin-22 (IL-22), IL6, tumor necrosis factor-a (TNF-a), serum endotoxin (=lipopolysacharide, LPS), adiponectin, serum zonulin, sCD14: soluble CD14 (endotoxin co-receptor), bile acids in serum and in stool, stool calprotectin and stool zonulin.

Vaginal samples will be taken using a cotton swab: eSwab™ (COPAN Italia S.p.A.) The swab will be inserted 5-6 cm beyond the vaginal orifice, and moved around along the vaginal wall for 10–15 s. The vaginal samples will be stored at -20°C and transported to a freezer at -80°C twice per week. Stool samples will be collected using a stool collection tube and stored in a cold transport container. Until further processing, samples will be stored in a freezer at -

20 °C immediately by the patient and at -80°C at the day the stool sample has arrived at Erasmus MC.

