4.3 Exclusion criteria

A potential subject who meets any of the following criteria will be excluded from participation in this study:

- BMI <18
- Smoking
- Diabetes Mellitus or use of insulin sensitizer
- Chronic and acute infection diseases
- Endometriosis (American Fertility Score (AFS) III/IV)
- Elevated prolactin levels, thyroid disease, Cushing disease or gastro-intestinal disease
- The use of hormonal contraceptives, other steroid hormones in last 3 months
- Use of antibiotics, probiotics or laxatives in the last 3 months

Control group:

- o After a COLA screening, subjects who have not been diagnosed with PCOS and have a regular menstrual cycle without hyperandrogenism or PCOM will have their dossiers individually evaluated to see whether they can participate in the control group.
 - o COLA screening volunteers who have already agreed to be approached for any future studies, will receive the PIF and be asked to participate in this study. These candidates are healthy and have a regular menstrual cycle.
 - o Online advertisement will be published to recruit volunteers.
- Inclusion criteria control group:
 - o Age 18-45years (premenopausal)
 - o Caucasian
 - o Willing to provide vaginal and stool sample
 - o Willing to provide informed consent
 - o Regular menstrual cycle (25-35days)
 - o Sufficient command of the Dutch language
 - o No history of diagnosed PCOS and do not meet any of the Rotterdam criteria.
- Exclusion criteria: see above.

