10.2 Secondary study parameter(s)

To analyse the association between the vaginal microbiome and PCOS compared to controls, the bacterial taxa will be first classified to the genus level. The relative abundance will be quantified based on each taxa contribution to an individual sample. Operational taxonomic unit (OTU) abundance will be noted for all samples. Alpha and Beta diversity will be calculated. Associations between the vaginal microbiome (Alpha and Beta diversity) and PCOS-associated variables as BMI, hirsutism, acne, testosterone, androstenedione, LH/FSH, insulin, will be tested in a linear regression model.

To investigate the association between the bacterial diversity and markers for gut permeability and inflammation in PCOS patients, a logistic regression model will be used. Leaky gut markers as calprotectin, zonulin, lipopolysaccharide and soluble CD15 and inflammation markers as CRP, IL-22, IL6 and TNF-a will be tested in the logistic regression model. Also the results of the Food Frequency Questionnaire (FFQ) will be analysed in the logistic regression model.

Differences on clinical characteristics and metabolic biomarkers will be evaluated using t-test or a one-way analysis of variance (ANOVA) for normally distributed variables or non-parameter Wilcoxon test for non-normally distributed variables. Two-sided tests will be used, and p-values less than 0.05 will be considered statistically significant.

As for the metabolomic analysis, the raw data will be pre-processed first. Log-transformation and centering are techniques used to make the data normal distributed. To investigate differences between the PCOS and controls, univariate analysis will be performed to examine each metabolite feature separately.

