15. Supplementary I

PCOS diagnose using the Rotterdam criteria by a presence of at least two of the following criteria:

- Oligomenorrhoea or amenorrhoea
- Clinical or biochemical hyperandrogenism (modified Ferriman-Gallway score ≥ 5 ; testosterone level $\geq 2\text{nmol/L}$, Free Androgen Index ≥ 2.9)
- Polycystic ovaries

Table 1

Phenotypes of PCOS according to the Rotterdam 2003 criteria

Features	Phenotypes			
	A	B	C	D
Ovulatory dysfunction	X	X	X	
Hirsutism and/or hyperandrogenemia	X	X		X
Polycystic ovaries	X		X	X

X, Features included in phenotypes

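### Sampling on any non-menstrual day leaves controls luteal more often than cases, so the vaginal comparison may partly reflect cycle phase, and cycle day at sampling is not among the listed data

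*Protocol*

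**What the plan says.** **Timing.** Protocol section 8.3: "Vaginal samples and blood samples will be collected in the non-menstrual period during the appointment". No cycle day or phase is fixed for either group. Stool is tied to the same appointment ("preferably on the day of the second appointment, but no more than 2 days before").

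**Controls.** Section 4.3 asks for regular cycles of 25 to 35 days and "No history of diagnosed PCOS and do not meet any of the Rotterdam criteria". It also excludes, in both groups, "The use of hormonal contraceptives, other steroid hormones in last 3 months". Controls are therefore expected to have natural, ovulatory cycles.

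**Cases.** They come from a clinic for cycle disorders (sections 4.1 and 8.3). One of the three diagnostic criteria in Supplementary I is "Oligomenorrhoea or amenorrhoea", and its Table 1 marks ovulatory dysfunction in phenotypes A, B and C but not D. The share of ovulatory cases is not given.

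**Measurements.** Section 8.3 lists a COLA panel that already contains LH, FSH and estradiol, and then: "Addition measurements that will be obtained include but will not limited to: LH, FSH, estradiol, progesteron". Section 12.1 extracts the menstrual cycle as an item from the clinical file, but names no cycle day at sampling.

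**Analysis.** The regressors named in 10.1 are the androgen measures, hirsutism, acne, BMI and LH/FSH. Section 10.2 gives a similar list for the vaginal microbiome, ending "androstenedione, LH/FSH, insulin, will be tested in a linear regression model". Neither names cycle day, phase, progesterone or estradiol.

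**The concern.** By ruling out menses, the protocol accepts that cycle timing matters for these samples, but it leaves the rest of the cycle open. A regularly ovulating woman spends a large part of her non-menstrual days in the luteal phase. A woman who is not ovulating spends none. Hormonal phase at the swab will therefore tend to differ between groups because of how the groups are defined, and a larger sample does not remove that.

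At stake is the interpretation of the vaginal case-control comparison. The protocol presents the relation of the vaginal microbiota to sex hormones as the gap it wants to fill (section 1). If a vaginal difference is found, a reader will ask whether it belongs to PCOS or to the cycle day. Without a recorded date of last menses, that question may be hard to answer afterwards.

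**Working it through.** The protocol states no figure on this point, so there is nothing to reproduce.

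**Inputs from the protocol:** control cycle length 25 to 35 days (4.3); any non-menstrual day allowed (8.3); 100 cases and 100 controls (section 3); two-sided 0.05 (10.2).

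**Assumptions, not in the protocol:** luteal phase 14 days (varied 12 to 14), menses 5 days (varied 4 to 7), visits equally likely on every non-menstrual day.

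**1. Luteal share in controls** = luteal days / (cycle length − menstrual days).

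| Cycle | Calculation | Luteal share |
|---|---|---|
| 25 days | 14/(25−5) | 70% |
| 28 days | 14/(28−5) | 61% |
| 30 days | 14/(30−5) | 56% |
| 35 days | 14/(35−5) | 47% |

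Varying both lengths, the extremes are 12/(35−4) = 39% and 14/(25−7) = 78%. Averaged evenly over cycles of 25 to 35 days, the share is 47% to 62%.

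**2. Luteal share among all cases** = o × 0.56 + (1 − o) × l. Here o is the share of cases that ovulate regularly (assumed 0 to 30%), and l is the luteal share among the rest. If none of the rest ovulate, l = 0. If every 60-day interval ended in ovulation, l = 14/(60−5) = 25%.
- Low end: o = 0 and l = 0 give 0%.
- High end: 0.30 × 0.56 + 0.70 × 0.25 = 0.168 + 0.175 = 34%.

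The high end is not a hard ceiling. Intervals of 42 days that all end in ovulation give l = 14/37 = 38%, and 0.168 + 0.70 × 0.38 = 43%.

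**3. Gap between groups**, at a control share of 56%: from 56 − 34 = 22 points to 56 − 0 = 56 points.

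**4. What a gap could do.** Bias in SD units = gap × d, where d is the luteal-phase shift in the outcome. The protocol gives no d, so the values below are illustrations only. With 100 per group the standard error is √(2/100) = 0.141 SD. The chance of p < 0.05 when PCOS has no effect is Φ(bias/0.141 − 1.96) + Φ(−bias/0.141 − 1.96). A comparison of two means stands in for the planned regression.

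| Gap | d (SD) | Bias (SD) | Chance of p < 0.05 |
|---|---|---|---|
| any | 0 | 0 | 5% |
| 0.25 | 0.2 | 0.05 | 6% |
| 0.45 | 0.3 | 0.14 | 16% |
| 0.45 | 0.5 | 0.23 | 36% |
| 0.45 | 0.8 | 0.36 | 72% |

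For scale, the difference detectable with 80% power is (1.96 + 0.84) × 0.141 = 0.40 SD.

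**5. Precision of a follicular-only comparison.** Controls kept: 100 × (1 − 0.70) = 30 to 100 × (1 − 0.47) = 53. With all 100 cases, the detectable difference is 2.80 × √(1/100 + 1/53) = 0.48 SD to 2.80 × √(1/100 + 1/30) = 0.58 SD. If only 66 cases are non-luteal, the least favourable value is 2.80 × √(1/66 + 1/30) = 0.62 SD.

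**The case against.** **An analysis plan may deal with this.** A statistical analysis plan that is not shown could add a phase analysis, so the absence of one in section 10 is not proof that none is planned. That stands. But an analysis plan cannot supply a date that was never collected, and data capture at the visit belongs to the protocol. The menstrual-cycle item in section 12.1 comes from the clinical file and does not clearly give cycle day at the swab.

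**A missing luteal phase is part of PCOS.** This also stands. A reader might infer that phase is a plain confounder and belongs as a covariate in the main models. The documents do not support that. Ovulatory dysfunction is a diagnostic criterion, so adjustment could remove part of the association under study, and with few luteal cases the term would be poorly estimated.

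**No phase effect is documented.** Correct. A reader might infer from step 4 that a false vaginal finding is likely, but those rates rest on assumed effects. At zero effect the error rate is the nominal 5%.

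**LH/FSH.** A reader might infer that mid-cycle LH in controls contaminates the regressions. LH and FSH are listed twice, once in the COLA panel and once as additional measurements, and sections 10.1 and 10.2 do not say which value is used. The cycle timing of the COLA blood is not stated either. What stands is that the source is unspecified. Estradiol is named in no comparison, so no claim is made about it.

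**Conclusion.** The point holds in a limited form. The timing rule permits a systematic difference in luteal exposure between groups: about 47% to 70% of control visits against about 0% to 34% among all cases. These figures assume random visit timing, a 14-day luteal phase, 5 menstrual days, at most 30% regularly ovulating cases and, for the upper end in cases, 60-day ovulatory intervals among the rest. The vaginal comparison may therefore partly reflect cycle phase, by an unknown and possibly small amount.

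A reader might extend this to the main endpoint. The documents do not support that: the main endpoint is the gut microbiome, and nothing in the protocol shows that stool results depend on phase. Nor does the point show that the vaginal comparison is invalid. It shows that the listed data may not let anyone judge how much phase contributes. It is worth fixing because it bears on the first secondary endpoint and the repair is cheap.

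**What to change.** - Record the date of last menses (cycle day) at the sampling visit in both groups, and add it to the data list in section 12.1.
- Classify phase using the progesterone already assayed, confirming that it is run on blood from the same visit as the swab. In amenorrhoeic cases the date alone will not settle phase.
- Keep visit timing and the main vaginal comparison as they are. Pre-specify one supportive comparison of cases not in the luteal phase with follicular-phase controls. Do not add phase as a covariate to the main case-control models.
- State whether LH/FSH in 10.1 and 10.2 comes from the COLA panel or the study visit. If it is the study visit, add a sensitivity analysis that accounts for phase.
- If phase is ever reported by phenotype, first reconcile the labels: section 1 calls hyperandrogenism with polycystic morphology phenotype C, and Table 1 calls it D.

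**Cost:** one recorded date and one extra analysis, plus a sensitivity analysis if LH/FSH comes from the study visit; no new sample or visit. The supportive comparison keeps only about 30% to 50% of controls, so its detectable difference rises from 0.40 SD to about 0.48 to 0.62 SD. A null result in it should not be read as showing that a main-analysis difference was due to phase.

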- To analyse the difference in gut- and vaginal microbiome composition between overweight/obese and lean (with/without PCOS).
- To analyse potential metabolic profiles characterizing different phenotypes of PCOS

Study design: A prospective observational case-control study, conducted at the Department of Obstetrics and Gynecology (Division of Reproductive Medicine) at the Erasmus University Medical Center Rotterdam

Study population: Patients with PCOS diagnosed based on the Rotterdam criteria must be Caucasian women, aged 18 - 45 years old (premenopausal), either overweight or obese (BMI>25) or lean (BMI18-25).

Main study parameters/endpoints:

The main parameter of this study is the differences in community structure (presence or absence of bacteria, alpha, and beta diversity) of the gut microbiome between PCOS patients and controls.

Secondary study parameters: 1. Differences in community structure (presence or absence of bacteria, alpha, and beta diversity) in the *vaginal* microbiome between PCOS patients and controls. 2. The differences and similarities between the vaginal- and gut microbiome composition in PCOS patients 3. The differences and similarities between the vaginal- and gut microbiome composition between overweight/obese and lean patients (with/without PCOS). 4. Metabolic profiles from different phenotypes of PCOS

Nature and extent of the burden and risks associated with participation, benefit, and group relatedness:

For all participants, the risks involve primarily the burden of participating in a study, which in the current study proposal means 1 additional hospital visit and assessments. Women from the study group have already undergone the regular physical examination (transvaginal ultrasound) and laboratory tests for the standard outpatient clinic for COLA (Cycle disorders, Oligomenorrhea and Amenorrhea) screening. Patients will be asked to collect a stool sample at home and bring or send this to the hospital. A vaginal sample will be obtained by a physician without using a speculum. The risks of participation are considered to be minor and there are no obvious risks associated with participation in the study. The assessment and determination of relevant gut and vaginal microbiome may lead to a better understanding of

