12. ADMINISTRATIVE ASPECTS, MONITORING ,AND PUBLICATION

12.1 Handling and storage of data and documents

Each subject will be assigned a study number. Data on microbiome composition will be stored anonymously and coded on basis of that study number. Only the coordinating investigators, project leader, and the principal investigator(s) will have access to patient identifying data and their respective study numbers. This is according to the EU General Data Protection Regulation and the Dutch Act on Implementation of the General Data Protection Regulation.

Storage of samples

Vaginal and stool samples will be frozen at -80°C and stored up to a maximum of 25 years.

Storage of data

Every patient will have to sign an informed consent form. All data will be stored and handled in the same way and according to the same rules and regulations as other patient-related data at the Erasmus MC. It will be stored as files on a separate research storage platform. Access will be limited to authorized study personnel. Should data transfer to other parties be necessary for testing or validation purposes, we will code the datasets and remove all personal data before the transfer. Data and information about the patient will be extracted from the clinical file. The signed consent forms must accompany the rectal and vaginal swab samples.

Data extracted from the clinical file are:

- Age
- Body Mass Index (BMI)
- Ethnicity
- Hirsutism or not (and Modified Ferriman Gallwey score)
- PCOM (polycystic ovarian morphology) or not
- Amenorrhea or oligomenorrhea
- Smoking / non-smoking
- Alcohol consumption
- Previous treatments for fertility
- Gynaecological history
- General health status and diseases
- Operations before treatment

- Menstrual cycle
- Previous use of antibiotics (estimated dates)
- Use of hormonal contraceptives

Data will be stored in a databank file in the Erasmus MC using Castor. Data will be further analyzed using analyzing and statistical software (e.g. R). The originally informed consent will be archived. Data sets used for analysis will be stored along with data analysis output and syntax files to facilitate control measures. These sets of data and files will be stored together with the versions of scientific publications reporting the findings of the study for an unlimited time.

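### PCOS cases recruited from the COLA database have no limit on the age of their COLA values and no stated re-measurement, so BMI, androgen and insulin data may be out of date, mainly in cases

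*Protocol*

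**What the plan says.** **Cases.** The protocol Summary states that the examination and laboratory work of cases precede the study: "Women from the study group have already undergone the regular physical examination (transvaginal ultrasound) and laboratory tests for the standard outpatient clinic for COLA". Section 8.3 gives the sequence for new patients: "Three to four weeks after the COLA screening patients will receive their COLA screening results", then "The main investigator will contact them by phone 1 week after their appointment for their COLA screening result", then a second appointment for the vaginal swab, blood and stool hand-in. Stool is collected close to that visit ("preferably on the day of the second appointment, but no more than 2 days before"). A second route follows in the same section: "Also, PCOS patients in the COLA database who are eligible will be approached to participate in this study". For this route the protocol states neither a maximum age of the COLA record nor a repeat of COLA.

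**Controls.** Section 8.3 says that for controls "the same COLA screening will be conducted, in combination with this study protocol". Section 4.3 adds that some controls come from women who have already been COLA-screened, and from earlier COLA volunteers.

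**Source of the values.** Section 8.3 lists total testosterone, androstenedione, SHBG, insulin and glucose among other assays and adds: "These laboratory measurements are already included in the COLA screening". The extra study assays name LH, FSH and estradiol again, but not the androgens, SHBG, insulin or glucose; that list is expressly open-ended. Section 12.1 says: "Data and information about the patient will be extracted from the clinical file", and the list that follows includes BMI and hirsutism.

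**Use of the values.** BMI defines the lean and overweight/obese groups (section 4.1; 50 of each among cases, section 3). Testosterone or FAI, androstenedione and BMI are predictors of gut diversity (section 10.1). BMI, testosterone, androstenedione and insulin are predictors of vaginal diversity (section 10.2).

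**The concern.** The outcome is a sample taken at the study visit. For a case from the database, the values set against it may date from a COLA visit of any age, and nothing in the protocol triggers a new one. Weight and insulin can change over such a period, and androgen levels may too.

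Two analyses are exposed. The regressions of diversity on BMI, androgens and insulin would use a predictor that differs from its value on the sampling day, which pulls the associations toward zero. The lean versus overweight/obese comparisons would place some women by a BMI that they no longer have. Controls, as section 8.3 is written, do not carry the same lag, so data quality would differ between the groups being compared.

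This is a data-collection matter. An analysis plan can choose between values or run sensitivity analyses, but it cannot recover a weight that was not measured or a hormone that was not assayed.

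**Working it through.** The protocol gives no figure on this point, and section 4.4 states no effect size, SD or power. There is therefore nothing to reproduce.

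**Step 1. Lag between COLA and sampling (section 8.3)**

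| Group | Lag |
|---|---|
| Newly diagnosed cases | 3 + 1 = 4 to 4 + 1 = 5 weeks, plus booking time |
| Cases from the COLA database | no upper limit |
| Controls, as section 8.3 reads | about 0 |
| Controls already COLA-screened (section 4.3) | not stated whether COLA is repeated |

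**Step 2. Which variables are exposed**

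- Named again at the study visit: LH, FSH, estradiol. The LH/FSH predictor is safe if the new values are used.
- Not named again: testosterone, androstenedione, SHBG (needed for FAI), insulin, glucose.
- BMI: clinical file, with no measurement date and no study-visit weighing stated.
- Not exposed: the unadjusted PCOS-versus-control comparison of diversity, which uses diagnosis alone.

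**Step 3. Illustration for a correlation.** All inputs are assumptions except n = 100 cases (section 3) and the two-sided 0.05 level (section 10.2). Model: COLA value = current value + independent error, with reliability λ, the squared correlation between the COLA value and the current one. The slope within cases is multiplied by λ and the correlation by √λ. Power = Φ(atanh(r√λ) × √(100 − 3) − 1.96), with assumed true r = 0.30.

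- λ = 1: atanh(0.300) × 9.849 = 3.048; 3.048 − 1.96 = 1.088; power 0.86
- λ = 0.9: r falls to 0.285; power 0.82
- λ = 0.7: r falls to 0.251; power 0.71
- λ = 0.5: r falls to 0.212; power 0.56

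These rows put the error in every case. If only a share f of cases has old values, overall reliability is 1/(1 + f(1/λ − 1)). With f = 0.5 (assumed) and λ = 0.9, 0.7, 0.5 this gives 0.947, 0.824, 0.667, and power 0.84, 0.79, 0.69.

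Section 10.1 also plans a Bonferroni correction. If it covers six tests (an assumed count), the critical value is 2.638 in place of 1.96. The four power figures above then become 0.66, 0.60, 0.46 and 0.30.

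**Step 4. Illustration for a pooled model.** In a large-sample simulation with error in cases only and equal predictor means in both groups, the pooled slope is multiplied by 0.95, 0.82 and 0.66 at λ = 0.9, 0.7 and 0.5. If the predictor is 1 SD higher in cases and the true slope is −0.3, a model adjusting for it leaves a false PCOS coefficient of −0.01, −0.06 and −0.10 SD. Under the same settings, error in both groups leaves more (−0.03, −0.09, −0.15). The harm thus comes from the error itself more than from its imbalance.

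**Step 5. Illustration for the BMI stratum.** The cut is 25 (section 4.1; section 4.4 gives other limits, which is a separate matter). COLA BMI is assumed N(22, 1.8) cut to 18-25 for lean and N(30, 4) above 25 for overweight/obese, with mean change zero.

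| SD of BMI change | Lean cases crossing 25, of 50 | Overweight/obese cases crossing 25, of 50 |
|---|---|---|
| 0.5 | 0.8 | 0.6 |
| 1 | 2.0 | 1.2 |
| 2 | 5.5 | 2.8 |
| 3 | 8.9 | 4.7 |

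The table applies the change to all 50 women in a group. With a share f of old records, multiply by f.

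**The case against.** The strongest reply is that the protocol is silent rather than wrong. It nowhere says that study-visit values will not be taken: blood is drawn at that visit, the list of extra assays is open, the Summary speaks of further assessments, and the clinical-file BMI carries no date. Database women must also be eligible, and eligibility includes a BMI limit (section 4.3), so a BMI check at enrolment is a fair reading. This stands as far as it goes: the use of old values is an inference. But permission to repeat an assay is not a plan to do so, and no weighing or interval limit appears anywhere.

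A reader might infer that the error sits in cases only. The documents do not support that, because section 4.3 also draws controls from women already screened. Section 8.3 does not say whether COLA is repeated for them or falls on the sampling day. Mainly in cases is as far as the text goes.

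A reader might also infer that all cases are affected. For new cases, 4-5 weeks plus booking should matter little, and the exclusion of insulin sensitizers and of hormonal contraceptives or other steroids in the last 3 months removes one source of change. That 3-month rule concerns medication; it does not limit the age of a COLA record.

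Finally, the objectives speak of diagnostic as well as metabolic characteristics. Values at diagnosis are a defensible measure of the former, so the timing point bears hardest on BMI and metabolic variables.

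**Conclusion.** The point holds for cases recruited from the COLA database: there is no interval limit and no stated re-measurement, while the values in question define the BMI strata and serve as predictors. The consequence is weaker covariate associations and some blurring of the BMI-stratified comparisons.

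The size cannot be derived from the protocol. It depends on the share of database cases, the age of their records and how far values move, and none of these is given. The illustrations run from negligible (reliability 0.9 in half the cases: power 0.84 against 0.86) to material (reliability 0.5 in all cases: 0.56). They should be read as that range and not as an estimate.

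It would be tempting to conclude that the main PCOS-versus-control result is biased. The documents do not support this: the unadjusted diversity contrast uses none of these variables. The false PCOS coefficient shown in the working arises only if a model adjusts the contrast for them. This is a worthwhile, inexpensive improvement to data collection, not a defect that undermines the study.

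**What to change.** 1. Measure height and weight of every participant, case and control, at the study visit. Use that BMI for the stratum and in all models.
2. Record the date of COLA and the COLA-to-sample interval in both groups.
3. Set a maximum interval in section 8.3. The choice of limit is a judgement for the investigators, since the protocol gives no basis for a particular value.
4. For anyone outside the limit, including controls screened earlier, assay testosterone, androstenedione, SHBG, insulin and glucose on the study-visit blood.
5. State in section 8.3 whether COLA is repeated for controls who have already been screened.

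The cost is a height and weight reading per participant at an existing visit, one date field, and a few routine assays on blood already drawn, for older records only.
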